8.2.2.2. Short Form Health Survey

The 36-item Short Form Health Survey (SF-36; Section 10.7, Appendix 7) will be administered through use of an eDiary. The Investigator should ensure that the Participant is provided with instructions and is trained to use the eDiary and to complete the assessment tool properly before data collection begins to measure the Participant's perception of their overall health status on the Day 270 and Day365/ET Visits. This 36-question survey measures the Participant's perception of vitality, physical functioning, bodily pain, general health perceptions, physical role functioning, emotional role functioning, social role functioning, and mental health.

Upon completion of the questionnaire, the study coordinator will check the questionnaire for completeness. Any omissions or ambiguous answers will be clarified by the Participant prior to leaving the clinic.

8.2.2.3. EuroOol Health Utilities Index

The EuroQol Health Utilities Index (EQ-5D) instrument (Section 10.8, Appendix 8) will also be administered through use of an eDiary. The Investigator should ensure that the Participant is provided with instructions and is trained to use the eDiary and to complete the assessment tool properly before data collection begins to measure the Participant's perception of their overall health status on the Day 270 and Day 365/ET Visits. The instrument has two parts – the descriptive system that measures mobility, self-care, usual activities, pain/discomfort, and anxiety/depression; and the visual analog scale (VAS) that records the Participant's self-rated health.

Upon completion of the questionnaire, the study coordinator will check the questionnaire for completeness. Any omissions or ambiguous answers will be clarified by the Participant prior to leaving the clinic.

Version 1.0 38 Final: 11 Feb 2021

8.2.3. Bedside Sensory Testing

Sensory tests will be performed at 3 predefined locations: dorsum of the foot, mid-shin, and mid-thigh, except low threshold mechanoreceptive function, which will be conducted at the bottom of the foot only on the Day 270 and Day 365/ET Visits. The Investigator should ensure that the Participant is seated comfortably before data collection begins.

The Bedside Sensory Testing is presented in Section 10.9, Appendix 9.

8.2.4. Michigan Neuropathy Screening Instrument

The Michigan Neuropathy Screening Instrument (MNSI) (Section 10.10, Appendix 10) will be administered through use of an eDiary (for the Participant) or an electronic tablet (for the Site) on Day 270 and Day 365/ET to track disease progression. The Investigator should ensure that the Participant is provided with instructions and is trained to use the eDiary and to complete the assessment tool properly before data collection begins. The MNSI comprises a Participant questionnaire (15 questions) and a physical evaluation that includes a foot inspection, vibration sensation testing, muscle stretch reflexes, and monofilament testing.

Upon completion of the MNSI questionnaire, the study coordinator will check the questionnaire for completeness. Any omissions or ambiguous answers will be clarified by the Participant prior to leaving the clinic. The Participant will be required to electronically sign and date the questionnaire.

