- 15. Treatment-emergent Adverse Events (TEAEs) will be monitored throughout the study and will be recorded after from the Day 180 Visit (VMDN-003-2) until Day 365/ET in this extension study. Any TEAEs that started during Study VMDN-003-2 and were ongoing at the Day 180 Visit will continue to be followed after Day 180 during this extension protocol. Adverse events that occur in this protocol will be referred to as TEAEs.

 Treatment-emergent Serious Adverse Events (TESAEs) will be recorded and reported to the Sponsor within 24 hours of awareness of the TESAE by the Site.
 - Adverse Events of Special Interest (AESIs): All AESIs will be continuously monitored throughout the study.
- **16. Michigan Neuropathy Screening Instrument (MNSI)** will be administered on Day 270 and Day 365/ET for assessing disease progression during the study.
- 17. **Bedside Sensory Testing (BST)** will be administered on Day 270 and Day 365/ET to provide additional information that will allow exploratory analysis of BST sensory profiles.

Version 1.0 Final: 11 Feb 2021

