8.3. Safety Assessments

8.3.1. Physical Examinations

Complete physical examinations (PEs) will be performed at the Day 270, Day 300, and Day 365/ET Visits; and at the last Visit if the Participant discontinues prior to Day 365. The complete PE will include the following: an examination of the skin/integumentary systems, general appearance, head, neck (including thyroid), eyes, ears, nose, throat, lymph nodes, chest (lungs), heart, abdomen, musculoskeletal system, neurological system, and any additional assessments needed to establish baseline status or evaluate symptoms or TEAEs. Any physical examination abnormalities considered to be clinically significant (CS) should be added to TEAEs using medically appropriate terminology.

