8.4.5.2. AESIs Related to Other Medical Problems

Several medical problems are frequently observed in patients with diabetic peripheral neuropathy that should be considered AESIs. These medical problems are listed below by type of medical problem.

Infections and Infestations; Skin and Subcutaneous Disorders

Because patients with diabetic peripheral neuropathy are at an increased risk to develop skin lesions (e.g., blisters, ulcers) and various lower limb infectious complications (e.g., cellulitis, osteomyelitis) that may be associated with systemic infections (e.g., bacteremia, sepsis, or septic shock), all of these types of medical problems that occur between the Day 180 (VMDN-003-02) and the Day 365/ET (VMDN-003-2b) Visits will be considered AESIs. In addition, any amputations involving the lower extremity, development of Charcot foot, or other similar complications will also be considered AESIs.

Peripheral Arterial Disease

An overlap of DPN and peripheral artery disease (PAD) apparently exists in type 2 diabetic patients. ⁴⁶ Because Participants with DPN may develop signs or symptoms of PAD between the Day 180 (VMDN-003-2) and the Day 365/ET (VMDN-003-2b) Visits, detailed evaluations of Participants considered to have PAD will be considered AESIs.

Version 1.0 43 Final: 11 Feb 2021

Diabetic Neuropathies

Because Participants in this study may develop other types of diabetic peripheral neuropathies while in the study, the following events will be considered to be AESIs in Participants with DPN: diabetic mononeuropathy, diabetic mononeuropathy multiplex, and diabetic polyradiculopathy. The occurrence of these other types of peripheral neuropathies in a Participant with DPN may indicate a more severe form of DPN.

Because Participants in this study may develop various manifestations of autonomic neuropathy (typically involves the gastrointestinal, genitourinary tract, cardiovascular systems) after randomization, the clinical manifestations of diabetic autonomic neuropathy will be considered to be AESIs.

Glycemic Control

Hypoglycemia, hyperglycemia, hyperlipidemia, hypercholesterolemia, and hypertriglyceridemia are to be listed as AESIs based on the Common Terminology Criteria for Adverse Events (CTCAE) grading if they are Grades 3 or 4.

Metabolic complications of DM (such as diabetic ketoacidosis [DKA], hyperglycemic hyperosmolar non-ketotic coma, lactic acidosis, metabolic acidosis [overlaps with DKA]) are to be listed as AESIs.

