10.10. Appendix 10. Michigan Neuropathy Screening Instrument

Patient Version

MICHIGAN NEUROPATHY SCREENING INSTRUMENT

A. His	tory (To	be completed	by the person	with diabetes)	
--------	----------	--------------	---------------	----------------	--

	Please take a few minutes to answer the following questions about the feeling in your legs and feet. Check yes or no based on how you usually feel. Thank you.						
1.	Are you legs and/or feet numb?	□ Yes					
2.	Do you ever have any burning pain in your legs and/or feet?	□ Yes	□ N				
3.	Are your feet too sensitive to touch?	☐ Yes					
4.	Do you get muscle cramps in your legs and/or feet?	□ Yes	□ N				
5.	Do you ever have any prickling feelings in your legs or feet?	☐ Yes	□ N				
6.	Does it hurt when the bed covers touch your skin?	□ Yes					
7.	When you get into the tub or shower, are you able to tell the						
	hot water from the cold water?	□ Yes					
8.	Have you ever had an open sore on your foot?	□ Yes	□ N				
9.	Has your doctor ever told you that you have diabetic neuropathy?	□ Yes					
10	. Do you feel weak all over most of the time?	□ Yes					
11	. Are your symptoms worse at night?	□ Yes	□ No				
12	. Do your legs hurt when you walk?	□ Yes					
13	. Are you able to sense your feet when you walk?	□ Yes	□ N				
14	. Is the skin on your feet so dry that it cracks open?	☐ Yes					
15	. Have you ever had an amputation?	□ Yes					

Total			
I Otal			

MNSI, © University of Michigan, 2000

Version 1.0 85 Final: 11 Feb 2021

MICHIGAN NEUROPATHY SCREENING INSTRUMENT

B. Physical Assessment (To be completed by health professional)

	 Appearance 	of Feet					
	a. Normal b. If no, ch					Left 0 Yes □ 1 that apply:	No
	Deformities Dry skin, ca Infection Fissure Other specify:	llus	□ □ □ □ Right		Deformities Dry skin, callus Infection Fissure Other specify:		
2.	Ulceration	Abs	ent Prese		Abser □ 0		sent ∃1
3.	Ankle Reflexes	Present □ 0	Present/ Reinforcement □ 0.5	Absent □1	Present □ 0	Present/ Reinforcement	Absent □1
4.	Vibration perception at great toe	Present 0	Decreased	Absent □1	Present □ 0	Decreased 0.5	Absent □1
5.	Monofilament	Normal □ 0	Reduced □ 0.5	Absent □ 1	Normal □ 0	Reduced □ 0.5	Absent □1
Sig	mature:			_	Total Score		_/10 Points

MNSI, © University of Michigan, 2000

Version 1.0 86 Final: 11 Feb 2021

How to Use the Michigan Neuropathy Screening Instrument

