History. The history questionnaire is self-administered by the Participant. Responses are added to obtain the total score. Responses of "yes" to items 1-3, 5-6, 8-9, 11-12, 14-15 are each counted as one point. A "no" response on items 7 and 13 counts as 1 point. Item #4 is a measure of impaired circulation and item #10 is a measure of general aesthenia and are not included in scoring. To decrease the potential for bias, all scoring information has been eliminated from the Participant version.

Upon completion of the questionnaire, the study coordinator will check the questionnaire for completeness. Note, the Participant will be asked to initial and date the questionnaire.

Physical Assessment. For all assessments, the foot should be warm (> 30°C).

Foot Inspection: The feet are inspected for evidence of excessively dry skin, callous formation, fissures, frank ulceration or deformities. Deformities include flat feet, hammer toes, overlapping toes, hallux valgus, joint subluxation, prominent metatarsal heads, medial convexity (Charcot foot) and amputation.

Vibration Sensation: Vibration sensation should be performed with the great toe unsupported. Vibration sensation will be tested bilaterally using a 128 Hz tuning fork placed over the dorsum of the great toe on the boney prominence of the distal interphalangeal (DIP) joint. Participants, whose eyes are closed, will be asked to indicate when they can no longer sense the vibration from the vibrating tuning fork. In general, the examiner should be able to feel vibration from the hand-held tuning fork for 5 seconds longer on his distal forefinger than a normal Participant can at the great toe (e.g., examiner's DIP joint of the first finger versus Participant's toe). If the examiner feels vibration for 10 or more seconds on his or her finger, then vibration is considered decreased. A study should be given when the tuning fork is not vibrating to be certain that the Participant is responding to vibration and not pressure or some other clue. Vibration is scored as 1) present if the examiner senses the vibration on his or her finger for < 10 seconds, 2) reduced if sensed for ≥ 10 or 3) absent (no vibration detection.)

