- Adverse events of special interest (AESI) by preferred term. An Excel spread sheet/listing will be generated for all TEAEs/TEAEs designated to be AESIs in the EDC database and sent to the Medical Monitors for review. The Medical Monitors will be blinded while reviewing the AESIs and will assign each AESI to one of the three main categories, including the subcategories for angiogenesis and AESIs related to other medical problems. When all AESIs have been assigned to a category by the Medical Monitors, the Excel spreadsheet/listing will be returned to the statistician. The statistician will break the blind and assign the participants with each of these AESIs to the appropriate treatment group and then, will generate appropriate tables and listings.

AESI summary tables will also be presented separately for each level of the randomization stratification factor.

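### MNSI foot inspection records ulceration and infection that overlap with AESIs, but no visible passage links these findings to AE reporting or to the safety tables

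*Protocol*

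**What the plan says.** Protocol 8.2.4 places the MNSI among the efficacy assessments. Its physical part is "a physical evaluation that includes a foot inspection, vibration sensation testing, muscle stretch reflexes, and monofilament testing", and footnote 16 of the Schedule of Activities says that the instrument "will be administered on Day 270 and Day 365/ET for assessing disease progression during the study". On the inspection itself, Appendix 10 (10.10) says: "The feet are inspected for evidence of excessively dry skin, callous formation, fissures, frank ulceration or deformities". For each foot, the printed form has an absent/present item for ulceration. Under appearance of the feet it has tick boxes for deformities, dry skin or callus, infection, fissure and other. The list of deformities is long and ends with "medial convexity (Charcot foot) and amputation".

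Protocol 8.4.5.2 makes skin ulcers and lower-limb infections arising between Day 180 and Day 365/ET AESIs, and adds that "any amputations involving the lower extremity, development of Charcot foot, or other similar complications will also be considered AESIs".

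Three other protocol passages bear on reporting:
- 8.3.1: "Any physical examination abnormalities considered to be clinically significant (CS) should be added to TEAEs". The examination takes place at Days 270, 300 and 365/ET.
- 8.4.9: disease-related events count as TEAEs, apart from a short list of neuropathy symptoms that includes neither ulcers nor infections.
- 10.2.1: abnormal findings associated with the underlying disease, and expected progression of the disease under study, are not AEs unless more severe than expected.

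In the visible SAP the MNSI appears in the missing-data rules of 10.6.2. The AESI summary in SAP 12.6.1 starts from events "designated to be AESIs in the EDC database". SAP 12.6 covers adverse events, vital signs, laboratory values, fundoscopy, ECG and acetaminophen. It has no MNSI output.

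**The concern.** Comparing safety between arms is a secondary objective, and foot ulcers and infections are among the events the protocol singles out for this population. The trial inspects both feet at two fixed visits in both arms, yet its AESI tables depend on whether each site separately entered the finding as an adverse event. If a site ticks ulceration on the MNSI form and makes no AE entry, no visible safety output shows it and no visible step looks for the mismatch.

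The plan handles a parallel case differently. New fundoscopic changes of proliferative retinopathy are AESIs (Protocol 8.4.5.1), and SAP 12.6.4 also tabulates the scheduled fundoscopy findings by arm, so the reported events can be read against a systematic examination. The visible plan does not do this for the feet.

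**Working it through.** The plan states no figure on this point, so the check is mainly a side-by-side reading.

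**1. Routes from scheduled assessments to safety outputs.**

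| Assessment | Stated route to the AE record | Output in SAP 12.6 |
|---|---|---|
| Physical examination | Protocol 8.3.1; SoA footnote 2 | None |
| ECG | Protocol 8.3.3; SoA footnote 4 | Listing (12.6.5) |
| Laboratory | Protocol 10.2.1 | Summaries and shift tables (12.6.3) |
| Fundoscopy | Protocol 8.4.5.1 | By-arm summary (12.6.4) |
| MNSI foot inspection | None that names the MNSI; 8.4.5.2 covers the event however it is found | None |

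**2. Path of a new ulcer ticked at Day 270.** It is an AESI under 8.4.5.2 and qualifies as a TEAE under 8.4.9. To reach a table it must be entered as a TEAE and flagged as an AESI in the EDC. The same-day physical examination can prompt that entry, with two weak points.
- 8.3.1 sends clinically significant abnormalities to the AE record, which is a judgement. SoA footnote 2 classes findings as significant or not and then asks for abnormalities to be recorded as AEs. Footnote 2 lists extremities and skin; 8.3.1 lists skin and the musculoskeletal system. Neither names the feet.
- 10.2.1 lets a finding associated with the underlying disease be left out unless it is more severe than expected. A foot ulcer in diabetic neuropathy could be read that way, particularly when the form's stated purpose is to follow disease progression. 8.4.5.2 and 8.4.9 point the other way.

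**3. The MNSI total score cannot stand in for an event count.** From the form in Appendix 10:
- Maximum score: 5 items per foot × 1 point × 2 feet = 10, matching the printed total.
- A new ulcer on one foot adds 1 point. An ankle reflex moving from absent (1) to present (0) removes 1. Net change: 1 − 1 = 0.
- Appearance of feet is one 0/1 item per foot. A new infection on a foot already scored abnormal for dry skin changes it by 1 − 1 = 0.

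**4. Imputation.** SAP 10.6.2 sets a missing ulceration item to present when the total is calculated. A count taken after that step would include events that nobody observed, so any safety table must use observed items.

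**5. Size.** Expected missing events per arm that the MNSI could recover = participants inspected × probability of a new ulcer or infection visible on a visit day × probability that it was not entered as an AE. The documents give none of the three; Protocol section 5 and SAP 8.1 leave even the extension's size open. No number follows.

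**The case against.** The strongest reply is that reporting is already mandatory. Section 8.4.5.2 applies whatever the source of the finding, 8.4.9 counts disease-related events, AESIs are to be monitored throughout, and a full physical examination falls on both MNSI visits and on Day 300. General checks also exist: source data verification (10.1.6.4), edit checks and manual review (10.1.7), and referral of questionable values to the blinded data review committee (SAP 10.0). A specific cross-form check may sit in the data management plan, which is not available here. All of this stands. It limits the point to a missing explicit link and reconciliation.

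The MNSI is also an imperfect measure of these AESIs. It shows what is present on two days within a period of 365 − 180 = 185 days, so an ulcer that heals between visits is not seen. Appendix 10 does not define the infection box.

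A reader might infer four stronger things that the documents do not support:
- **That the MNSI serves solely as an efficacy score.** The text of SAP 12.5.4 is redacted and may include item-level summaries.
- **That deformity as a class is an AESI.** The single deformity box also covers flat feet and hammer toes, which 8.4.5.2 does not name, and it cannot identify Charcot foot.
- **That a stated share of events is lost.** Any percentage would only restate an assumed capture rate.
- **That the gap biases the comparison of arms.** Participants, investigators and site staff are blinded (6.1.3), so incomplete entry gives no evident reason for a difference between arms. The safety analysis is descriptive.

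**Conclusion.** The point holds as a minor improvement in safety ascertainment. MNSI ulceration and infection items overlap with named AESIs, no visible passage links them to AE reporting or to SAP 12.6, and the AESI tables use only events already designated in the EDC. Reporting is required by other routes, but it passes through a clinical-significance judgement and through an exclusion in 10.2.1 that conflicts with 8.4.5.2 and 8.4.9. Some events that the trial measures could therefore be absent from its safety tables. Their number cannot be estimated from the documents, and no omission of harm has been shown. The conclusion rests on the visible text; a reconciliation step in the data management plan would meet part of it.

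**What to change.** 1. In SAP 12.6, add a descriptive by-arm shift table (absent to present, either foot) for MNSI ulceration and for MNSI infection at Days 270 and 365. Use observed values only, without the worst-case rule of 10.6.2. Take the Day 180 MNSI as reference if VMDN-003-2 collected one, otherwise Day 0, and state which. SAP 12.6.4 already uses a main-study reference for fundoscopy. If Day 0 is used, a shift may have begun before the TEAE period, which SAP 12.6.1 starts on the day after the Day 180 visit, so the table should not be labelled as TEAEs.
2. Before database lock, run a blinded listing of new MNSI ulceration or infection with no matching AE, and query the site, including the onset date. Query deformity entries only to ask whether they are Charcot foot or amputation; do not tabulate them as safety events.
3. Reconcile the exclusion in Protocol 10.2.1 with 8.4.5.2 and 8.4.9, so that sites have one reading for foot findings.

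The cost is one table, one listing and a clarification, all from data already collected. The downside is a few more data queries.

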8.3. Safety Assessments

8.3.1. Physical Examinations

Complete physical examinations (PEs) will be performed at the Day 270, Day 300, and Day 365/ET Visits; and at the last Visit if the Participant discontinues prior to Day 365. The complete PE will include the following: an examination of the skin/integumentary systems, general appearance, head, neck (including thyroid), eyes, ears, nose, throat, lymph nodes, chest (lungs), heart, abdomen, musculoskeletal system, neurological system, and any additional assessments needed to establish baseline status or evaluate symptoms or TEAEs. Any physical examination abnormalities considered to be clinically significant (CS) should be added to TEAEs using medically appropriate terminology.

8.3.2. Medical History and Familial History of Cancer

Medical history for this extension study will be based on the medical history information recorded at Screening for Study VMDN-003-2.

Medication history will be based on recorded medications within 30 days prior to the Day 180 Visit of Study VMDN-003-2.

Elevated risks of cancer for type 2 diabetes or obesity are detailed in Section 8.4.5, Adverse Events of Special Interest.

Version 1.0 39 Final: 11 Feb 2021

Helixmith Co., Ltd. CONFIDENTIAL VMDN-003-2b

8.3.3. 12-Lead Electrocardiograms

12-Lead electrocardiograms (ECGs) will be performed on Days 270 and 365/ET. Any clinically significant abnormalities are to be reported as adverse events. The ECG recording will be printed, and the investigator or delegated staff will initial and date the printout to indicate their review of the findings. The trace and the interpretation will then be stored with the Participant's records.

8.3.4. Vital Signs

Vital signs will be measured at the Day 270, 300, and 365/ET Visits. After resting in the seated position for 5 minutes, vital signs measured will include temperature, sitting blood pressure, heart rate, respiratory rate, and oxygen saturation on room air. The method of temperature measurement should be according to the Site's policy and should be consistently applied.

